8.4.3 Pregnancy and assessments of fertility

All pre-menopausal women who are not surgically sterile will have pregnancy testing at screening (serum), at randomization (Day 1, before administration of study medication (urine)), and every 4 weeks thereafter (urine). Where the visit interval is greater than 4 weeks, or in the case that the participants cannot visit the site, the participants will be provided with urine pregnancy tests kits to be used at home. Results must be provided to the investigator at the next scheduled visit. Participants should be instructed to perform the urine pregnancy test first and only if the test result is negative proceed with the administration of the study treatment.

[figure not shown]
A positive urine pregnancy test needs to be confirmed with a serum test. Where a home urine pregnancy test is positive the participant must contact the investigator and return to site for a serum pregnancy test, in the case that participants cannot visit the site an alternative (local lab) can be used. If positive the participant must be discontinued from study treatment. If participants are not able to perform a home urine pregnancy test (e.g., if prohibited by local regulations), a urine or serum test can be performed at the local laboratory as directed by the investigator.

A communication process should be established with the participant so that the site is informed and can verify the pregnancy test results (e.g., following country-specific measures).

Additional pregnancy testing might be performed if requested by local requirements.

Assessments of fertility

Medical documentation of oophorectomy, hysterectomy, or bilateral tubal ligation must be retained as source documents. Subsequent hormone level assessment to confirm the woman is

not of child-bearing potential must also be available as source documentation in the following cases:

1. Surgical bilateral oophorectomy without a hysterectomy
2. Reported 12 months of natural (spontaneous) amenorrhea with an appropriate clinical profile.

In the absence of the above medical documentation, FSH testing is required of any female participant regardless of reported reproductive/menopausal status at screening/baseline.

8.4.4 Appropriateness of safety measurements

[figure not shown]
The selected safety monitoring assessments (including laboratory assessments covering clinical chemistry, hematology, coagulation status and immunoglobulins, as well as clinical and physical assessments, triplicate ECG monitoring and general AE assessments) are reliable and well-established standard measures which allow valid and close safety monitoring of the trial's patient population, with regards to their disease, to the compound they are treated with, remibrutinib, and also to their overall medical safety.

[figure not shown]
[figure not shown]
8.5 Additional assessments

[figure not shown]
8.5.1 Clinical Outcome Assessments (COAs)

Trial Feedback

This study includes an optional anonymized questionnaire, the 'Trial Feedback Questionnaire' for trial participants to provide feedback on their clinical trial experience at 3 timepoints: at the start, during and at the end of the trial. Individual trial participant responses will not be reviewed by investigators. Responses may be used by the sponsor to understand where improvements can be made in the clinical trial process. This questionnaire does not ask questions about the trial participant's disease, symptoms, treatment effect or adverse events and therefore is not considered as trial data.

9 Discontinuation and completion

9.1 Discontinuation from study treatment and from study

[figure not shown]
9.1.1 Discontinuation from study treatment

Discontinuation of study treatment for a participant occurs when study treatment is permanently stopped for any reason (prior to the protocol planned completion of study drug administration) and can be initiated by either the participant or the investigator.

The investigator must discontinue study treatment for a given participant if, he/she believes that continuation would negatively impact the participant's well-being.

Discontinuation from study treatment is required under the following circumstances:

- Participant decision (requested in writing or verbally)

- Pregnancy
- Use of prohibited treatment requiring study treatment discontinuation as detailed in [Table 6-3](#) or discontinuation of highly effective methods of contraception as detailed in [Section 5.2](#)
- Any situation in which continued study participation might result in a safety risk to the participant
- Following emergency unblinding
- Emergence of the following AEs:
 - any adverse events that in the judgement of investigator, taking into consideration the participant's overall status, prevents the participant from continuing participation in the study, including:
 - hypersensitivity reactions,
 - severe/serious infections,
 - clinically significant spontaneous bleeding events
 - new confirmed diagnosis of malignancy of any organ system
(other than localized basal cell carcinoma of the skin or in situ cervical cancer)
 - Platelets < 75 000/mm³
 - Abnormal renal laboratory results requiring discontinuation (see [Section 16.3](#))
 - Abnormal liver laboratory results requiring discontinuation (see [Section 16.2](#))
 - Any other laboratory abnormalities that in the judgment of the investigator, taking into consideration the participant's overall status, prevents the participant from continuing participation in the study
 - participant received a live virus vaccination during the study

[figure not shown]
If discontinuation from study treatment occurs, the investigator should make a reasonable effort to understand the primary reason for the participant's discontinuation from study treatment and record this information.

All participants who discontinue from study treatment prematurely should complete the Early treatment discontinuation visit at the time of treatment discontinuation.

For participants who discontinue from study treatment prior to week 12, where possible they should be requested to return for visits after the Early treatment discontinuation visit as per the Assessment Schedule ([Table 8-1](#)) up to and including the week 12 timepoint. At the week 12 timepoint the study discontinuation visit should be performed [REDACTED]. If the participant declines to continue with assessments as per the visit schedule up to week 12, then they should complete the safety follow-up visit after the Early treatment discontinuation visit.

Participants who discontinue from study treatment after week 12 should complete the safety follow-up visit indicated in the Assessment Schedule ([Table 8-1](#)) whenever possible.

If the participant cannot or is unwilling to attend any visit(s), the site staff should maintain regular telephone contact with the participant, or with a person pre-designated by the participant. This telephone contact should preferably be done according to the study visit schedule.

After discontinuation from study treatment, at a minimum, in abbreviated visits, the following data should be collected at clinic visits or via telephone/email contact:

- New / concomitant treatments
- Adverse Events / Serious Adverse Events

The investigator must also contact the IRT to register the participant's discontinuation from study treatment.

If discontinuation occurs because treatment code has been broken, please refer to Emergency breaking of treatment code section.

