to Week 24 (which is beyond the primary endpoint at Week 12) will provide a background incidence in the study population for possible safety findings and will ensure a valid assessment of the durability of the treatment response. It will support a more robust characterization of the safety profile of remibrutinib, i.e., if safety events are observed in both the placebo and remibrutinib arms, it may be inferred that the events are not necessarily related to the study treatment. To limit the duration of placebo treatment, the placebo-controlled treatment period will stop at Week 24, since a period of 24 weeks allows a reliable and valid assessment of efficacy and safety in patients with CSU.

3. **Open-label treatment period:** during this treatment period of 28 weeks, all participants will receive open-label remibrutinib (25 mg b.i.d.). Together with the preceding double-blind, placebo-controlled period, a total of up to 52 weeks of remibrutinib (25 mg b.i.d.) treatment will be studied within this trial. This is in line with current CSU treatment guidelines (Zuberbier et al 2018) and will provide adequate long-term efficacy and safety data to fully characterize the value of remibrutinib (25 mg b.i.d.) in CSU treatment. Switching placebo treated participants to active treatment with remibrutinib at Week 24 gives all participants the opportunity to receive active treatment with remibrutinib within the course of this study.
4. **Follow-up period:** a treatment-free follow-up period of four weeks at the end of the study will be implemented for all participants who do not enroll into the extension study (currently in planning stage). This allows the assessment of safety of treatment discontinuation as well as the dynamics of potential re-occurrence of CSU signs and symptoms after treatment discontinuation.

The study population consists of participants with CSU (UAS7 score ≥ 16 , with HSS7 score ≥ 6 and ISS7 score ≥ 6), who have a duration of CSU of ≥ 6 months and who are inadequately controlled despite treatment with second generation H1-antihistamines at least at locally label approved dose. Importantly, patients who have inadequately responded to or did not tolerate anti-IgE biologic treatments are also eligible for this study. Thus, CSU patients with a high unmet medical need are the target population for this study.

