6.1.4 Treatment duration

The planned duration of treatment is 52 weeks. Participants may discontinue from study treatment earlier at the discretion of the investigator or the participant, e.g., due to adverse events (see [Section 9.1](#)) or lack/loss of efficacy. Eligible participants may roll over into the planned extension study at Week 52 (after completing all scheduled assessments planned at these visits). The details of the study design and procedures of the extension, if implemented, will be described in a separate protocol.

There are a total of 9 dispensing visits per participant in the trial, 6 in the double-blind period and 3 in the open-label period. The last dispensing visit occurs at Week 40.

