Open label	Week 25	-	Day 1 (Date of first study treatment in open-label period) to Day 7 of open-label period
	Week 26	-	Day 8 to Day 14 of open-label period
	Week 27	-	Day 15 to Day 21 of open-label period
	Week 28	-	Day 22 to Day 28 of open-label period
	Week 29	-	Day 29 to Day 35 of open-label period
	Week 30	-	Day 36 to Day 42 of open-label period
	Week 31	-	Day 43 to Day 49 of open-label period
	Week 32	225	Day 50 to Day 56 of open-label period
	Week 33	-	Day 57 to Day 63 of open-label period
	Week 34	-	Day 64 to Day 70 of open-label period
	Week 35	-	Day 71 to Day 77 of open-label period
	Week 36	-	Day 78 to Day 84 of open-label period
	Week 37	-	Day 85 to Day 91 of open-label period
	Week 38	-	Day 92 to Day 98 of open-label period
	Week 39	-	Day 99 to Day 105 of open-label period
	Week 40	281	Day 106 to Day 112 of open-label period
	Week 41	-	Day 113 to Day 119 of open-label period
	Week 42	-	Day 120 to Day 126 of open-label period

	Week 43	-	Day 127 to Day 133 of open-label period
	Week 44	-	Day 134 to Day 140 of open-label period
	Week 45	-	Day 141 to Day 147 of open-label period
	Week 46	-	Day 148 to Day 154 of open-label period
	Week 47	-	Day 155 to Day 161 of open-label period
	Week 48	-	Day 162 to Day 168 of open-label period
	Week 49	-	Day 169 to Day 175 of open-label period
	Week 50	-	Day 176 to Day 182 of open-label period
	Week 51	-	Day 183 to Day 189 of open-label period
	Week 52	365	Day -7 to Day -1 of Week 52 study visit

Note: Week 52 study visit is during treatment epoch. eDiary data on this day will not be taken into the analysis.

For participants early discontinued study treatment prior to Week 12, it is suggested to collect the eDiary data even after the participant discontinued from treatment per “Treatment policy strategy” (this part of data is named as “retrieved drop-out data”). The retrieved drop-out (RDO) data will be included in the weekly score derivation until Week 12, when treatment policy strategy is used for estimands.

For participants who discontinued the study treatment earlier than Week 24, assessment will follow rules as defined in [Table 2-4 up to Week 24](#). After Week 25, weekly scores will not be derived even when the eDiary data are collected.

Table 2-4 Assessment window for weekly scores based on eDiary (for early treatment discontinued participants earlier than Week 24)

Analysis period	Analysis visit	Scheduled Visit Day	eDiary Assessment Window
Double blind	Baseline	1	Day -7 to Day -1

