5.4.2.3 Negative binomial regression

Count variable including the cumulative number of weeks achieving AAS7= 0 response between baseline and Week 12 or the cumulative number of weeks achieving UAS7≤6 response will be modelled using a negative binomial regression model with log link, using treatment group, randomization strata factors (i.e. geographic region and prior exposure to anti-IgE biologics, and baseline AAS7=0 status (for AAS7 = 0 response only). The patient's time in the treatment period up to Week 12 (natural log of proportion of time in treatment period, i.e., natural log of [number of weeks with the response variable in treatment period/12 weeks]) is used as an offset variable. The patient's time in the treatment period up to Week 24 (natural log of proportion of time in treatment period, i.e., natural log of [number of weeks with the response variable in treatment period/24 weeks]) is used as an offset variable.

If the AAS7 = 0 (respectively UAS7≤6) assessment is missing, it will be considered as a non-response for the cumulative number of weeks that participants achieve AAS7= 0 response calculation (respectively UAS7≤6).

The negative binomial model accounts for any over dispersion that may result from assuming a Poisson distribution by allowing a different Poisson rate for each patient and assuming that these rates as a set are distributed across participants according to a gamma distribution.

The SAS procedure PROC GENMOD will be used for this analysis with the following code:

```
proc genmod data=...;  
  by impnb;  
  class trt01p antige region/ param = glm;  
  model count = baseline trt01p antige region/ DIST= NEGBIN LINK= LOG  
  offset=offset;  
  lsmeans trt01p / cl exp diff ilink e OM;  
  estimate "LOU064 v.s pbo" trt01p 1 -1;
```

```
ods output Estimates=estimates LSMeans=lsmeans;
run;
```

where baseline = baseline AAS7=0 status (for AAS7 = 0 response only).

The SAS procedure PROC MIANALYZE will be used to combine the results. The risk ratio and the 95% confidence interval for the risk ratio will be generated using an exponential transformation of the model estimates.

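### Efficacy data after stopping treatment are not planned between Weeks 12 and 24, so Week 24 durability results will rest on participants still on treatment and on imputation

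*Protocol*

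**What the plan says.** **Purpose.** Protocol section 4.1 says that placebo control to Week 24, beyond the Week 12 primary endpoint, "will ensure a valid assessment of the durability of the treatment response". It gives background incidence for safety findings as a further reason.

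**Collection (Protocol 9.1.1 and Table 8-1).**
- "All participants who discontinue from study treatment prematurely should complete the Early treatment discontinuation visit at the time of treatment discontinuation". Table 8-1 has DLQI and eDiary review at that visit.
- Those who stop before Week 12 are asked to keep attending to Week 12, and then "At the week 12 timepoint the study discontinuation visit should be performed" (a short redaction follows).
- "Participants who discontinue from study treatment after week 12 should complete the safety follow-up visit indicated in the Assessment Schedule". Table 8-1 shows neither DLQI nor eDiary review at the safety follow-up visit.
- "After discontinuation from study treatment, at a minimum, in abbreviated visits, the following data should be collected at clinic visits or via telephone/email contact": the list is concomitant treatments and adverse events, with no efficacy item.
- The eDiary runs until Week 52 or study discontinuation, but 9.1.1 schedules no study discontinuation visit for those who stop after Week 12.

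**Reasons for stopping.** Protocol 6.1.4: "Participants may discontinue from study treatment earlier at the discretion of the investigator or the participant", with lack or loss of efficacy among the examples.

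**Analysis.**
- SAP 2.1.1.1 analyses efficacy by initial randomisation up to Week 24.
- SAP 2.1.1.5: "For participants who discontinued the study treatment earlier than Week 24, assessment will follow rules as defined in" Table 2-4, whose windows run to Week 24. The same section uses retrieved drop-out (RDO) data in weekly scores only until Week 12.
- SAP 5.4.2.3 has an offset for "The patient's time in the treatment period up to Week 24".

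**The concern.** The plan commits to a placebo-controlled look at durability but stops asking for efficacy data from those whose durability is most in doubt. Because lack or loss of efficacy is an expected reason for stopping, being unobserved at Week 24 is likely to depend on outcome. A comparison among those who remain is then no longer protected by randomisation. A treatment-policy comparison can still be calculated, but with almost no post-discontinuation data after Week 12 its result would be driven by the imputation assumption, with little in the trial to test that assumption against.

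**Working it through.** **1. The plan's own figure.** Protocol 12.8.1 states more than 99% power for UAS7 at Week 12 with 270 against 135, difference 10, SD 12 and one-sided 0.025. SE = 12 × √(1/270 + 1/135) = 1.265; 10/1.265 = 7.91; 7.91 − 1.96 = 5.95; power > 0.9999. It reproduces. The point does not concern power and disputes no stated figure.

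**2. Collection against analysis, Weeks 13–24.**

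| Participant | Efficacy data requested | What the visible SAP does |
|---|---|---|
| Still on treatment | Daily diary, scheduled visits | Weekly scores to Week 24 |
| Stopped before Week 12 | None after Week 12 | Table 2-4 windows to Week 24; RDO data used to Week 12 |
| Stopped after Week 12 | Discontinuation visit only | Table 2-4 windows to Week 24; a discontinuation-visit DLQI on Days 86–169 is mapped to Week 24 |

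The missing-data rules in SAP 2.5.1.3 and 2.5.1.4 (intercurrent events, the 50% check on whether RDO data are sufficient, other missing data) all refer to Week 12. If the same check were used at Week 24, RDO data would be scarce by design. The choice would then fall to jump-to-reference (J2R) for remibrutinib and missing-at-random for placebo.

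**3. How many participants.** The documents give no Week 24 rate. If the planned 10% drop-out per 12 weeks also described stopping treatment and continued (assumption), 1 − 0.9² = 19% would be off treatment by Week 24. That is 450 × 0.19 ≈ 85 participants, of whom 450 × (0.90 − 0.81) ≈ 40 stop after Week 12.

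**4. Mean UAS7 difference among stayers.** Assume a true difference of 10 (the plan's Week 12 figure) and stoppers g points worse than stayers in both arms. Stayers' mean = arm mean − f × g, where f is the fraction stopping. The shift in the difference is therefore g × (f_active − f_placebo).
- 10% active, 20% placebo, g = 4 to 12: −0.4 to −1.2.
- 20% active, 10% placebo: +0.4 to +1.2.
- Equal stopping: 0.

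**5. If stopping also removes effect.** The zero in step 4 needs the same shortfall in both arms, which means that stoppers keep the full difference. If the difference is 10 in stayers and 0 to 5 in stoppers, with equal stopping, the difference over everyone randomised is (1 − f) × 10 + f × (0 to 5):
- f = 10%: 9.0 to 9.5
- f = 19%: 8.1 to 9.05
- f = 25%: 7.5 to 8.75

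Power stays above 99% in each case.

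**6. UAS7 ≤ 6 rates, extreme case.** Take the planning rates of 53% and 15% and assume that every stopper is a non-responder. With 5% to 10% stopping:
- Remibrutinib: 0.53/0.95 = 55.8% to 0.53/0.90 = 58.9%, a rise of 2.8 to 5.9 points.
- Placebo: 0.15/0.95 = 15.8% to 0.15/0.90 = 16.7%, a rise of 0.8 to 1.7 points.

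**The case against.** The strongest reply is that the SAP does not discard stoppers. Efficacy uses the Full Analysis Set as randomised, any diary data that stoppers provide are scored to Week 24, discontinuation visits are remapped to scheduled visits, and missing data are imputed whenever a model is fitted. A reader might infer that the Week 24 comparison is made only among those who stay on treatment; the documents do not support that. Nor do they support the inference that remibrutinib's durability must look too good: J2R would pull remibrutinib stoppers towards placebo, and step 4 shows that the stayers' difference can move either way. It would also be wrong to expect a similar absolute shift in the placebo response rate; step 6 shows a much smaller one for the same stopping rate.

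Second, every tested efficacy endpoint is at Week 12 or earlier, and RDO follow-up matches that target. This stands in full.

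Third, the SAP's amendment log records the addition of a Week 24 estimand, and parts of the SAP are redacted. Rules for Weeks 13–24 may exist out of sight, and their absence from the visible text is not held against the plan. However, an estimand cannot supply data that section 9.1.1 does not request.

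Fourth, the discontinuation visit does capture efficacy. It records status at stopping, though, not the course afterwards.

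**Conclusion.** The point holds as a gap between a stated purpose and the data collected for it. After the discontinuation visit (for those who stop after Week 12) or after Week 12 (for those who stop earlier), no efficacy data are planned. Observed Weeks 13–24 summaries will mostly describe participants on treatment, and modelled Week 24 estimates will depend on imputation whose visible rules reach only Week 12.

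The direction and size of any bias cannot be determined, because they turn on arm-specific stopping rates that the documents do not give. Under the assumptions shown, the mean UAS7 difference among stayers shifts by 0 to 1.2 points either way when the shortfall is the same in both arms. With 19% off treatment, a difference of 10 in stayers corresponds to 8.1 to 9.05 over all randomised participants if stoppers lose half or more of the effect. The primary and secondary tests are not affected. This is an inexpensive improvement to a supporting comparison, not a threat to the trial's main result.

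**What to change.** 1. **Protocol 9.1.1:** ask every participant who stops study treatment before Week 24 to continue the home eDiary to Day 168, with no added site visits, and define that as the end of their diary. This covers UAS7, ISS7, HSS7 and AAS7; DLQI is completed at visits and would still be missing.
2. **SAP 2.1.1.5:** extend the use of RDO data in the Table 2-4 windows from Week 12 to Week 24.
3. **SAP 2.5.1.3 and 2.5.1.4:** state the intercurrent-event and missing-data rules for Weeks 13–24, including how medication that the protocol allows after Week 12 is handled in the analysis. Without this, the extra diary data would be hard to interpret.
4. **If collection is already complete:** report the Week 24 results with a missing-data sensitivity analysis, and qualify the durability claim as resting mainly on participants still on treatment and on imputation.

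The cost is amendment wording plus at most 12 further weeks of home diary for those who stopped by Week 12, and fewer for later stoppers. The device is already issued and the windows already exist. The downsides are some participant burden and incomplete uptake, so imputation will be reduced but not removed.

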² Serum pregnancy test and fertility assessment will be done at Screening. Urine pregnancy test to be completed every 4 weeks by WoCBP from Randomization through Study completion visit. At Weeks 28, 36, 44 and 48 test may be performed at home - sites must contact participants to obtain test results. Any positive or undetermined test result must be confirmed by a serum pregnancy test done by central lab and results obtained electronically. Urine pregnancy results are reported as source. If participants are not able to perform a home urine pregnancy test (e.g., prohibited by local regulations), a urine or serum test can be performed at the local laboratory.

³ Participants eDiary will be returned to site at either week 52/study discontinuation.

⁴ Complete physical exam at screening, short physical exam at all subsequent visits including body temperature monitoring (per local practice)

⁵ Height collected at screening visit only

⁶ pre and post dose

⁷ eDiary includes UPDD (Urticaria Patient Daily Diary) with UAS (Urticaria Activity Score, part of UPDD) and AAS (Angioedema Activity Score), eDiary to be completed from screening to week 52/study discontinuation

⁸ Completed in the patient's eDiary during site visit. Order of completion: DLQI [REDACTED]. All questionnaires should be completed prior to any other physician assessment.

[REDACTED]

¹⁴ Hepatitis B re-activation monitoring only for participants who were HBsAg negative and HBcAb (anti-HBc) positive with a negative HBV DNA test at Screening.

[figure not shown]
[REDACTED]

[REDACTED]

Period	Screening	Treatment											Follow-up	Unscheduled visit	
Visit Name	Screening	Baseline/ Randomization ¹	week 2 ¹	week 4	week 8	week 12 ¹	week 16	week 20	week 24	week 32	week 40	Early treatment discontinuation	week 52/Study discontinuation ¹	week 56/Safety FU/Study completion	Unscheduled visit
Days	-28 to -1	1	15	29	57	85	113	141	169	225	281		365	394	-

¹⁶Dispensation for background medication covers prescription, dispensation and/or instruction of the participant on dosing and use of background medication and protocol requirements, considering different procedures for the provision of background medication at investigational sites. At Week 56/Safety FU/Study completion visit only compliance to be checked

¹⁷ Only for participants who have completed Week 52 visit, not applicable at Study discontinuation visit

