8.3 Efficacy

8.3.1 eDiary assessments

All participants will be provided with an electronic device (eDiary) that contains the following Patient Reported Outcomes (PRO) assessments: Urticaria Patient Daily Diary (UPDD) and Angioedema Activity Score (AAS).

Site and participants will receive appropriate training and guidance on the use of the eDiary and will receive clear instructions on the completion of the assessments.

Assessments will be completed twice daily (UPDD), once daily (AAS, if triggered by opening question within the UPDD) from screening to week 52/study discontinuation.

In general, participants complete eDiary questionnaires at home and independent of study visits. Participants will be instructed to complete eDiary entries after they took their study medication throughout the treatment period.

[figure not shown]
The DLQI, [REDACTED] questionnaires will be administered during respective visits on site and should be completed prior to any other study specific procedure. Site personnel must allow participants to complete the questionnaire on their own without any assistance from the site staff. In the case that participants cannot come to site (see Section 4.6), the DLQI, [REDACTED] will be available on their electronic device.

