12.4.3 Handling of intercurrent events of primary estimand

Participants who discontinue from study treatment early due to any reason will be encouraged to stay in the study following the procedures. Every effort will be made to continue to follow participants who discontinued from study treatment up to Week 12. These are considered as Retrieved drop out (RDO) participants.

The analysis will account for different intercurrent events as explained in the following:

- Discontinuation of study treatment prior to Week 12 due to any reason: ignore (Treatment policy strategy), i.e., data collection will be maintained and available measurements post-treatment discontinuation will be used as if they had been obtained under the treatment assigned at randomization: RDO data collected after study treatment discontinuation will be used for analysis.
- Intake of rescue medication as per protocol, or switch of background medication, or intake of other prohibited medication, or participants non-compliant to treatment prior to Week 12: ignore (Treatment policy strategy), data collected after these events will be used for analysis.
- Intake of strongly confounding prohibited medication (e.g., biologics treatment at any time before Week 12, cyclosporin after Week 8, systemic corticosteroids after Week 8): (Composite strategy) measurements after this event will be excluded from the analysis and will be imputed using the worst value of the endpoint (e.g., 42 for UAS7 score at week 12 and 21 for co-primary endpoints ISS7 score or HSS7 score at week 12).

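### For early treatment discontinuers who decline the visit schedule or are followed only by telephone, the minimum data set omits the home eDiary that alone supplies Week 12 UAS7, ISS7 and HSS7

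*Protocol*

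**What the plan says.** **What the analysis needs.** Protocol Sections 2.1 and 12.4.3 handle discontinuation of study treatment by a treatment policy strategy: "RDO data collected after study treatment discontinuation will be used for analysis". Section 12.4.3 also commits to following discontinuers up to Week 12. For those who stop before Week 24, SAP Table 2-4 takes the Week 12 score from diary Days 78 to 84. Protocol Section 12.4.4 and SAP Section 2.5.1.1 require at least 4 non-missing daily scores.

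**How the diary is run.** Protocol Section 8.3.1: "In general, participants complete eDiary questionnaires at home and independent of study visits". That section and Table 8-1 footnote 7 run the diary from screening to Week 52 or study discontinuation. On the device, Table 8-1 footnote 3 says: "Participants eDiary will be returned to site at either week 52/study discontinuation".

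**What Section 9.1.1 asks after treatment stops before Week 12.**
- Default: scheduled visits continue through Week 12, where the study discontinuation visit is done (some text after this is redacted).
- Decliners: "If the participant declines to continue with assessments as per the visit schedule up to week 12, then they should complete the safety follow-up visit", directly after the early treatment discontinuation (ETD) visit.
- Unable or unwilling to attend visits: regular telephone contact, preferably on the visit schedule.
- Minimum data: "After discontinuation from study treatment, at a minimum, in abbreviated visits, the following data should be collected at clinic visits or via telephone/email contact". The list has two items, "New / concomitant treatments" and "Adverse Events / Serious Adverse Events".

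**What the SAP adds.** Section 2.1.1.5 says of these participants that "it is suggested to collect the eDiary data even after the participant discontinued from treatment". Section 2.5.1.4 lets the share of an arm's discontinuers with Week 12 retrieved drop-out (RDO) data decide how the missing cases are imputed. At 50% or more, imputation uses RDO data. Below 50%, it is jump-to-reference for active and MAR for placebo.

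**The concern.** The estimand asks what happened at Week 12 whether or not the participant stayed on treatment, and the only instrument that answers this needs no clinic visit. Section 9.1.1 nonetheless builds follow-up around visits and site contacts. A site can follow it to the letter, send a decliner to safety follow-up or telephone an absentee, and never ask for the diary. A participant who would have kept a home diary then has no Week 12 UAS7, ISS7 or HSS7, and no later diary weeks for the two cumulative-week endpoints.

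At stake are how many Week 12 outcomes are imputed when they could have been observed, and which imputation route the SAP then selects for the arm.

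**Working it through.** **1. Follow-up routes set against the endpoint**

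| Route after stopping before Week 12 | Diary in Section 9.1.1? | Days 78-84 likely available? |
|---|---|---|
| Default: visits to Week 12 | Implied; diary runs to study discontinuation | Generally yes |
| Declines the visit schedule | No; safety follow-up next | Not requested |
| Telephone contact only | Not in the minimum list | Depends on the site |
| Study discontinuation visit on Day 80 or earlier | Diary and device end at that visit | No (step 2) |

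**2. Early study discontinuation visit.** If diary completion ends at a Day 80 visit, scores can exist only for Days 78, 79 and 80. That is 3, below the required 4, so Week 12 UAS7 is missing. SAP Section 2.1.1.5 uses a Day 80 study discontinuation visit in its own example and maps it to Week 12. That mapping is for site-visit assessments; diary weeks for these participants are fixed by study day.

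**3. The plan's own power figure** (Protocol Section 12.8.1: 270 v 135, one-sided 0.025, stated power above 99%).
- UAS7: standard error 12 × √(1/270 + 1/135) = 1.265; 10/1.265 = 7.91; power above 99.99%.
- ISS7 and HSS7: 6 × √(1/270 + 1/135) = 0.632; 4/0.632 = 6.32; power 99.999%.

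The stated figure reproduces.

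**4. Ceiling on numbers.** Assume that all of the planned 10% are treatment discontinuers before Week 12 and none supplies Week 12 data: 0.10 × 300 = 30 active and 0.10 × 150 = 15 placebo.

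**5. Ceiling on the estimate.** If a share m of active participants is imputed by jump-to-reference, the expected difference is about (planned difference) × (1 − m). With 300 v 150, the standard errors are 12 × √(1/300 + 1/150) = 1.2 for UAS7 and 0.6 for ISS7 or HSS7 (SD held fixed).

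| m | UAS7 difference | ISS7/HSS7 difference | Power |
|---|---|---|---|
| 0 | 10 | 4 | >99.9% |
| 0.05 | 9.5 | 3.8 | >99.9% |
| 0.10 | 9.0 | 3.6 | >99.9% |
| 0.20 | 8.0 | 3.2 | >99.9% |

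The largest fall at the planned 10% is 10 − 9.0 = 1.0 UAS7 point.

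**6. The 50% rule.** With 30 and 15 discontinuers, the rule needs at least 15 active and 8 placebo participants with Week 12 RDO data. Let v be the share retained by visits and h the share of the rest who would keep only the diary. The probability of having data is q = v + (1 − v)h, and the chance of meeting the rule is a binomial tail. Both v and h are assumptions; the documents give neither.

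| v | h | q | P(at least 15 of 30 active) | P(at least 8 of 15 placebo) |
|---|---|---|---|---|
| 0.3 | 0 | 0.300 | 0.017 | 0.050 |
| 0.3 | 0.25 | 0.475 | 0.462 | 0.422 |
| 0.3 | 0.5 | 0.650 | 0.970 | 0.887 |
| 0.4 | 0 | 0.400 | 0.175 | 0.213 |
| 0.4 | 0.25 | 0.550 | 0.769 | 0.654 |
| 0.4 | 0.5 | 0.700 | 0.994 | 0.950 |
| 0.5 | 0 | 0.500 | 0.572 | 0.500 |
| 0.5 | 0.25 | 0.625 | 0.944 | 0.841 |
| 0.5 | 0.5 | 0.750 | 0.999 | 0.983 |

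If visit retention is around half or less, diary-only follow-up could decide which imputation route an arm takes.

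**The case against.** The strongest reply is that the diary is already scheduled past treatment discontinuation. Diary completion and device return are tied to study discontinuation, and the glossary describes a treatment discontinuer as agreeing to the remaining assessments. The two-item list is a floor for what sites gather at contacts, whereas the diary is entered by the participant. This stands for the default path. A reader might infer that Week 12 data are lost for early discontinuers generally, and the documents do not support that.

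Other points that stand:
- The decliner route is triggered by refusing assessments on the visit schedule, which is broader than refusing to travel. Some decliners would refuse the diary too.
- Week 12 is scheduled for Day 85, and Protocol Section 8 asks for visits close to the designated day. A Day 80 visit is five days early, and the redacted text in Section 9.1.1 may bear on its timing.
- As extracted, the eDiary dispensing row of Table 8-1 carries an entry at the ETD visit. One might infer that the device is collected then. The column position comes from extracted text and footnote 3 says otherwise, so this needs clarifying but does not show a contradiction.
- Jump-to-reference pulls the active arm towards placebo, so it does not flatter the drug.
- An SAP does not instruct sites.

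None of this supplies a diary step for participants who decline the schedule, or tells a site to ask for the diary from someone it only telephones.

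**Conclusion.** The point holds for three groups: decliners of the visit schedule, participants followed only by telephone, and those whose study discontinuation visit falls on Day 80 or earlier. For them, the plan as written can replace obtainable primary-endpoint data with imputation.

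The size cannot be derived from the documents. The 30 and 15 participants and the 1.0-point fall are upper bounds. They assume the planned 10% drop-out, that every drop-out is a treatment discontinuer before Week 12 with no diary data, and, for the 1.0 point, jump-to-reference for all 30 active cases. Reading 1.0 point as the expected bias would go too far. So would inferring a threat to power, which stays above 99.9% even at 20%. What is affected is the reliance on imputation and the chance of meeting the 50% rule. It is worth changing because the remedy is specific and cheap.

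**What to change.** - **Protocol Section 9.1.1:** add the UPDD/AAS eDiary through Day 84 to the minimum data for anyone stopping treatment before Week 12. Ask those who decline visits to continue the home diary only. Have the device kept until Day 85 or later.
- **Table 8-1:** clarify that the ETD entry in the eDiary dispensing row does not mean device return for participants who agree to continue, consistent with footnote 3.
- **SAP Section 2.1.1.5:** replace the suggestion with wording that matches the protocol requirement. The protocol change is the one that collects data.

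The cost is a wording amendment, a modest diary burden for at most 12 weeks, and later device return. The device is already with the participant. The DLQI is administered at site visits, so this change does not by itself recover it.

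The current SAP is dated 24-Jan-2024 and labelled as preceding the final analysis, so Week 12 collection may already be over. In that case the wording cannot recover data here. The useful step would be to report, by arm and follow-up route, how many discontinuers before Week 12 had Week 12 diary scores.
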